We expect that this parent-based behavioural sleep intervention will improve the sleep quality of children with ADHD, which in turn may lower inattention/hyperactivity impairment, reduce parental stress and improve the child's daily functioning.

Objectives and Hypothesis of the study

To assess the effect of a brief parent-based sleep behavioural intervention on the sleep quality as well as other aspects of functioning and mental health of children with ADHD and their parents.

Compared to children with ADHD and insomnia receiving treatment as usual, the group of children with ADHD and insomnia receiving the parent-based intervention will have better sleep and functioning as well as parental mental health at post-intervention and follow-up at 3 months.

Study Design/Methodology

Study Sites

Alice Ho Miu Ling Nethersole Hospital, TaiPo, N.T., Hong Kong

Sleep Research Clinic & Laboratory, Department of Psychology, The University of Hong Kong

Study Population

Parents of children who meet all the following inclusion criteria and none of the exclusion criteria will be our target participants.

Inclusion criteria:

ADHD with sleep problem(s)

- Aged 6-12 years old;
- With a clinical diagnosis of ADHD (any subtype), as confirmed by the Diagnostic Interview Schedule for Children-version-IV (DISC-IV);
- With parent-reported insomnia (difficulty initiating sleep and/or maintaining sleep).

Exclusion criteria:

1. Children with a serious medical condition (e.g. severe cerebral palsy) or intellectual disability (IQ<70);
2. Children with a neurological and/or medical condition that may lead to disordered sleep;
3. Suspected clinical sleep disorders (e.g. obstructive sleep apnea, OSA) that may potentially contribute to a disruption in sleep continuity and quality, as assessed by the Children's Sleep Habits Questionnaire (CSHQ). If the child is suspected of a clinical sleep disorder, he/she will be

referred to appropriate services;

4. Children who are already receiving specialized help for their sleep from a psychologist or at a specialized sleep clinic.

A total of 60 families will be invited to participate in this programme and will be randomized into intervention group and waitlist-control group (30 families each).

Subject Recruitment Plans and Consent Process

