Demographics & health history. Each family will complete a brief questionnaire so as to provide sample characteristics of the child (demography, family characteristics, medical history). Prescribed medication(s) of the child at the time of study will be documented and recorded.

Evaluation survey. Each family will be invited to complete a brief evaluation survey to provide feedback on the usefulness and arrangement of the intervention.

Measures on sleep, ADHD symptoms, other clinical symptoms and functioning, and cognitive performance of the child, as well as parental sleep and mental health will be administered at the following time-points for the intervention and waitlist-control group: before the intervention programme (baseline); after the intervention (one-week after the follow-up call to assess the short-term effects of the intervention). The above measurements will be additionally conducted for the intervention group at 3 months after the intervention to assess any long-term effects of the treatment.

Statistical Analysis Plan

Sample Size Determination and Power

The primary outcome is the child's sleep based on parental report (e.g. CSHQ, sleep problems rated by parents), as a measure of intervention efficacy. Secondary outcomes include other sleep measures (e.g. actigraphic parameters, daytime sleepiness), daytime functioning, quality of life and other

clinical symptoms and behavior of the child, as well as parental sleep and mental health. A previous representative study found an effect size of -0.8 for CSHQ at 3 months follow-up, which would require 26 families in each arm to have 80% power at the two-sided 5% level of significance to detect this effect.⁴⁹ To allow for 15% loss to follow-up, we require 30 families in each group.

Analysis Plan

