Preliminary descriptive analysis will be conducted to compare the two groups (intervention, wait-list control) for any baseline differences in sleep and functioning characteristics. Subsequent analysis will be conducted on an intention to treat basis. For child- and parent-related measures, changes between baseline and post-intervention as well as between baseline and follow-up at 3 months will be computed. Mean differences in change at 95% confidence interval in outcomes between intervention and control arms will be estimated with regression models, adjusting for covariates as well as baseline scores for each specific measure if there are any group differences.⁵⁰ Potential covariates to be considered include the child's age, sex, medication use (yes or no), and family socioeconomic status (measured by monthly family income). As for computing effect sizes, changes in each outcome will be standardized to a mean of 0 and standard deviation of 1, before repeating the regression analyses. Effect sizes are interpreted as small, moderate and large for standard deviations of ~0.20, 0.50, and .80 respectively.⁵¹

Declaration of Helsinki

The study will follow the ethical principles under the Declaration of Helsinki. The right of all individuals to self-determination and the right to make informed decisions regarding participation in research, both initially and during the course of the research are respected. Participants' welfare would take precedence over the interests of science and society, and ethical consideration would take precedence over laws and regulations.

Privacy and confidentiality

Participants' names will be kept on a password-protected database and will be linked only with a study identification number for this research. There are no patient identifiers. Data will be stored in a locked office of the investigators and maintained for a minimum of three years after the completion of the study.

Risk/Benefit to participants

This study does not present any risks to the participants. Selected participants will all receive a behavioural sleep intervention and related education materials.

References

1. Clinical practice guidelines: diagnostic and evaluation of the child with attention deficit/hyperactivity disorder. American Academy of Pediatrics Committee on Quality Improvement. *Pediatrics* 2000; 105, 1158-1170.

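### Standardising change over both arms puts the treatment effect into the SD, so moderate and large effect sizes are slightly understated (0.80 becomes about 0.74)

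*Protocol*

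**What the plan says.** The Analysis Plan section of the protocol sets the main estimate: "Mean differences in change at 95% confidence interval in outcomes between intervention and control arms will be estimated with regression models". It then gives a separate rule for effect sizes: "changes in each outcome will be standardized to a mean of 0 and standard deviation of 1, before repeating the regression analyses". The coefficients from that second run are labelled as follows: "Effect sizes are interpreted as small, moderate and large for standard deviations of ~0.20, 0.50, and .80 respectively". The section does not say over which children the standardising SD is taken, and it mentions no within-arm, control-arm or baseline SD. Allocation is equal, with 30 families per arm (Study Population).

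**The concern.** A standardised effect size is usually meant to express the difference between arms in units of the spread among comparable children. If the SD is taken over both arms together, part of that spread is the treatment difference itself, so the unit grows with the effect being measured.

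That the SD spans both arms is an inference, but a firm one. Standardising each arm separately to mean 0 would set both arm means to 0 and force the unadjusted difference to exactly zero, leaving nothing to estimate.

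At stake are the size and label of the standardised effects for the child and parent outcomes. The tests and the estimates in scale units are not at stake.

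**Working it through.** **Inputs.** From the protocol: equal arms of 30 (Study Population); z-scored change and benchmarks of 0.20, 0.50 and 0.80 (Analysis Plan); an effect of 0.8 in absolute value, 80% power, two-sided 5% and 26 families per arm (Sample Size Determination and Power). Assumed: equal within-arm SDs of change (set to 1) and no covariate adjustment.

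**1. The plan's own figure.** A two-sample t-test with d = 0.8, 80% power and two-sided 5% needs 25.52 per arm, so 26 (power 0.807). The stated 26 is reproduced.

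**2. Expected value under the stated rule.** With 1:1 arms and a true difference d, the variance over both arms is 1 + d²/4. The z-scored coefficient is therefore about d/sqrt(1 + d²/4). For d = 0.80: sqrt(1 + 0.64/4) = sqrt(1.16) = 1.077, and 0.80/1.077 = 0.743.

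| Effect in within-arm SDs | Expected report | Shrinkage |
|---|---|---|
| 0.20 | 0.199 | 0.5% |
| 0.50 | 0.485 | 3.0% |
| 0.80 | 0.743 | 7.2% |
| 1.00 | 0.894 | 10.6% |

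Imbalance hardly matters: at 40:60, 0.80 becomes 0.745.

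**3. Effect needed to reach a benchmark.** Inverting, e/sqrt(1 − e²/4): a report of 0.50 needs 0.516, and a report of 0.80 needs 0.873. Only within-arm effects of 0.50 to 0.516, or 0.80 to 0.873, would drop below a benchmark.

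**4. What happens in a sample.** Let SSW be the within-arm sum of squares. With 30 per arm, the pooled variance is SSW/58 and the both-arm variance is SSW(1 + t²/58)/59. So the reported value equals the pooled-SD value times sqrt(59/(58 + t²)), where t² = 15d² for an observed pooled-SD value d. The factor exceeds 1 when |t| < 1, that is, when |d| < sqrt(1/15) = 0.258.

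- d = 0.10: t² = 0.15, reported 0.1007
- d = 0.20: t² = 0.60, reported 0.2007
- d = 0.50: t² = 3.75, reported 0.489
- d = 0.80: t² = 9.60, reported 0.747

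In simulation with 30 per arm, the reported value was the larger of the two in 68% of data sets at a true effect of 0, 55% at 0.20, 17% at 0.50 and 2% at 0.80.

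**5. Mean estimate at a true 0.80.** Over 200,000 simulated trials with 30 per arm, the mean was 0.740 with the both-arm SD and 0.811 with the pooled within-arm SD. The small-sample factor is 1 − 3/(4×58 − 1) = 0.987, and 0.811 × 0.987 = 0.800.

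**6. Size against sampling error.** The standard error at 0.80 with 30 per arm is sqrt(2/30 + 0.64/120) = 0.268. The shift is 0.80 − 0.743 = 0.057, and 0.057/0.268 = 0.21.

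**7. What does not move.** Z-scoring is a linear rescaling. In a check data set the p-value for the arm difference was 0.000575 both before and after it.

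**The case against.** The rule is defined and reproducible, and a difference in SDs of the observed change is a legitimate descriptive scale. The benchmarks are marked as approximate and name no particular SD. The choice between an SD of change and a baseline SD can also matter more. If the SDs before and after treatment are equal and correlate at r (an assumption, since the protocol gives no r), an effect of 0.80 baseline SDs is 0.80/sqrt(2(1 − r)) SDs of change: 0.68, 0.80 or 1.03 at r = 0.3, 0.5 or 0.7. Finally, naming the exact SD is often left to a statistical analysis plan.

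Most of this limits the size of the point without removing it. The protocol does not leave the standardiser open. It states a procedure whose divisor depends on the treatment effect, and a baseline or pooled within-arm SD would avoid that. The comparison of standardisers is a good reason to name the SD in the report.

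Three stronger readings are tempting but not supported:

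- *Every reported effect size is shrunk.* This holds for the population formula but not for sample values. Below about 0.26 the reported value is very slightly larger than the pooled-SD value.
- *The reported effect sizes are on a different scale from the planning value.* The sample-size section says only this about its source: "A previous representative study found an effect size of -0.8 for CSHQ at 3 months follow-up". It does not say which SD was used, so no mismatch can be shown.
- *The trial's power or its test of efficacy is affected.* Neither is, because the rescaling leaves the test unchanged.

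**Conclusion.** The point holds as a minor one. Under the stated rule, moderate and large standardised effects are understated on average: by about 3% at 0.50, 7% at 0.80 and 11% at 1.00. For effects of that size the direction is conservative. The shift at 0.80 is about one-fifth of a standard error. A label changes only if the approximate benchmarks are applied as hard cuts and the within-arm effect lies in one of the narrow bands just above a benchmark.

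The figures rest on equal arms, equal within-arm SDs, an unadjusted coefficient, and the reading that one SD spans both arms. Covariate or baseline adjustment can change the numerator but does not take the treatment effect out of the divisor. No conclusion about efficacy depends on this.

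**What to change.** Do not z-score the change over both arms. Take the adjusted between-arm mean difference in change and its 95% confidence limits from the main regression, and divide them by the pooled within-arm SD of change for that outcome. Multiply by the small-sample factor 1 − 3/(4×df − 1), which is 0.987 at 58 degrees of freedom and 1 − 3/199 = 0.985 if 26 families per arm remain (50 degrees of freedom). Name the SD beside the effect sizes and apply the approximate labels to that value. Add a note that the scaled interval treats the SD as known.

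The cost is a sentence or two in the Analysis Plan. The data, the model and the sample size stay the same. The change concerns the standardiser only. It does not resolve which time points allow a comparison between arms: the protocol adds the 3-month measurements for the intervention group alone, and that is a separate question.

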Appendix

Figure 1.

Recruitment criteria (for psychiatrists' reference):

Inclusion criteria:

- 6-12 years old (of both genders)
- ADHD (any subtype)
- With insomnia (difficulty initiating and/or maintaining sleep)

Excluding those with the following condition

- Serious medical condition (e.g. severe cerebral palsy) or intellectual disability (IQ<70)
- Neurological and/or medical condition that may lead to disordered sleep
- Clinical sleep disorders (e.g. obstructive sleep apnea, OSA)
- Receiving specialized help (behavioural intervention) for their sleep from a psychologist or at a specialized sleep clinic
